6.6 Reporting and Exclusions

Compliance will be monitored closely. Non-compliant patients who use the treatment fewer than 2 times a day for more than 2 weeks (as determined by review of the treatment diary at the week 4 visit) will be considered unevaluable for the primary endpoint and replaced with new patients. These patients, however, will be included in the toxicity report. During the four-week period when patients are receiving study treatment, additions of new immunomodulatory medications (systemic or topical in the mouth) are allowed, but these patients will be regarded as unevaluable for the primary endpoint and will be replaced.

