2.1 Study Design

This is a single center, 4-week, open label randomized, phase II study. Randomization will be conducted by the BWH Investigational Pharmacy. The study period will be four weeks, which based on previous studies should be an adequate period to assess significant clinical improvement. Subjects will be evaluated clinically at baseline before starting treatment and at the end of the four-week period, for a total of two visits. Subjects will be randomized to either compound dexamethasone in Mucolox™ or dexamethasone only. Subjects will return for evaluation after four weeks at which time the primary end-points will be assessed.

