5. STUDY PROCEDURES

Potentially eligible subjects will be screened by one of the investigators by asking patients to rate their worst oral pain or pain score (0-10) over the previous week (see Appendix). Those answering with at

CONFIDENTIAL

This document is confidential. Do not disclose or use except as authorized.

least a score of “7” (1/10) and that meet all other eligibility requirements (see Section 3) will be eligible for enrollment. All patients will sign informed consent for study participation. Each study visit is anticipated to take approximately 45 minutes. A urine pregnancy test will be performed for women of child bearing potential.

There is no financial compensation for participating in this study. Treatment will be administered on an outpatient basis. Study medication will be prescribed by authorized study staff physicians and filled by the BWH Investigational Pharmacy at no expense for the patient. No investigational or commercial agents or therapies other than those described below may be administered with the intent to treat the participant’s oral lichen planus.

Subjects will be evaluated clinically at baseline before starting treatment and at the end of the four-week period, for a total of two visits. Comprehensive subjective and objective data will be collected (Appendix 3 & 4) and intraoral photographs will be obtained. Oral mucosal disease will be evaluated using both patient reported (questions/visual analog scales) and clinician assessed measures.

Subjects will be prescribed compound dexamethasone 0.5mg/5ml solution in Mucolox™ (ARM A) or dexamethasone 0.5mg/5ml solution only (ARM B). All subjects will also receive a prescription for fluconazole 200 mg tablets once-a-week as prophylactic antifungal therapy. Any subjects that are already taking an antifungal oral medication at the time of the study enrollment will continue their prescribed medication and will not need to take the additional weekly fluconazole dose. Subjects will return for evaluation after four weeks at which time the study end-points will be assessed.

Clotrimazole or Nystatin will be prescribed as an alternative antifungal drug in the event of fluconazole allergy.

If there is worsening of oral lichen planus that requires initiation of new immunomodulatory medications (systemic or topical), patients will remain on treatment, but will be regarded as unevaluable for the primary endpoint.

	Day 1 (baseline)	Day 28 ± 5 days (end of study)

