5.6 Criteria for Taking a Participant Off Protocol Therapy

Subjects will be taken off protocol therapy for any of the following reasons:

- If the principal investigator feels it is in their best interest
- If the subject cannot tolerate the study rinses
- Intercurrent illness that prevents further administration of treatment
- Unacceptable adverse event(s)
- Participant demonstrates an inability or unwillingness to comply with the oral medication regimen and/or documentation requirements
- Participant decides to withdraw from the protocol therapy
- General or specific changes in the participant's condition render the participant unacceptable for further treatment in the judgment of the treating investigator

Participants will be removed from the protocol therapy when any of these criteria apply. The reason for removal from protocol therapy, and the date the participant was removed, must be documented in the case report form (CRF). Alternative care options will be discussed with the participant.

Subjects may be removed from the study in favor of clinical care should their symptoms worsen or should they have an adverse reaction to the study drug.

In the event of unusual or life-threatening complications, treating investigators must immediately notify the Overall PI [name], PhD, MPH at [contact] ([name]).

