5.8 Criteria for Taking a Participant Off Study

Participants will be removed from study when any of the following criteria apply:

- Lost to follow-up
- Withdrawal of consent for data submission
- Death

The reason for taking a participant off study, and the date the participant was removed, will be documented in the case report form (CRF).

6. BIostatistical Analysis

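### Patients who add an immunomodulator or under-use the rinse after randomisation are dropped from the primary endpoint and replaced, and no all-randomised primary analysis is specified

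*Combined protocol and SAP*

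**What the plan says.** Section 6.6 (Reporting and Exclusions) names two groups.

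- **Under-users.** Patients rinsing less than twice daily over more than two weeks "will be considered unevaluable for the primary endpoint and replaced with new patients". This is judged at the end of the study, "as determined by review of the treatment diary at the week 4 visit".
- **Patients who add an immunomodulator** (systemic, or topical in the mouth) during the four weeks. The addition is allowed, but "these patients will be regarded as unevaluable for the primary endpoint and will be replaced".

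Section 5 (Study Procedures) gives the reason for the second exclusion: "If there is worsening of oral lichen planus that requires initiation of new immunomodulatory medications (systemic or topical"). Those "patients will remain on treatment, but will be regarded as unevaluable for the primary endpoint". Section 5 does not mention replacement; only Section 6.6 does.

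Section 2.1 sets the design: "This is a single center, 4-week, open label randomized, phase II study". The primary endpoint (Sections 5.1.3 and 6.1) is the change in the patient's own worst-sensitivity score, 0 to 10, from baseline to week 4. Section 6.4 compares the change between arms by t-test or Mann-Whitney test and names no analysis set. The only statements covering all patients concern toxicity (Sections 6.6 and 6.6.1). No missing-data method is given. Section 6.2 allows 5% for loss to follow-up and does not mention replacements.

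**The concern.** Both exclusions depend on events after randomisation. The first depends on the disease getting worse, and the endpoint is reduction in symptoms of that disease, so it can remove treatment failures from the comparison. Clinician and patient both know the assignment, so the decision to add a drug can also depend on the arm. Replacement restores the count of 12 per arm but not the comparison that randomisation created.

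At stake is the trial's single primary test. If one arm loses more of its poor responders, that arm looks better than it is. If the vehicle works and failures leave mainly Arm B, part of a real benefit is hidden.

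**Working it through.** **Inputs.** From Section 6.2: mean reductions of 6.5 (Arm A) and 4.5 (Arm B), SD 1.4, two-sided alpha 0.05, power at least 80%, 12 per arm, 5% loss. From Section 6.4: t-test on the change. Exclusion rates are not in the documents. The rates below are assumptions chosen to correspond to a few replaced patients: 14.3% is 2 of 14, 7.7% is 1 of 13, 25% is 4 of 16, 8.3% is 1 of 12.

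**1. The plan's sample size.** At n per arm the noncentrality is 2.0 / (1.4 × √(2/n)).
- The t-test needs 9 per arm (power 81.2%); 9/0.95 = 9.5, so 10 with 5% loss.
- With the lower-bound Mann-Whitney efficiency of 0.864: 9/0.864 = 10.4, so 11; 11/0.95 = 11.6, so 12, the stated figure.
- At 12 per arm the noncentrality is 2.0 / (1.4 × 0.408) = 3.50 and t-test power is 91.7%.

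**2. Worst-case bias with no true difference.** Suppose the lowest share q of responders is excluded and replaced until 12 are evaluable. With z the q-quantile of the standard normal and φ its density, the arm's mean rises by 1.4 × φ(z) / (1 − q):
- q = 14.3%: 1.4 × 0.2258 / 0.857 = 0.369
- q = 7.7%: 1.4 × 0.1444 / 0.923 = 0.219
- q = 25%: 1.4 × 0.3178 / 0.75 = 0.593
- q = 8.3%: 1.4 × 0.1529 / 0.917 = 0.233

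The bias is the difference between arms. Error rates are from simulation (200,000 runs, N(4.5, 1.4) in both arms).

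| Excluded | Bias (points) | Error favouring the arm with more exclusions (nominal 2.5%) | Two-sided error (nominal 5%) |
|---|---|---|---|
| 14.3% v 7.7% | 0.369 − 0.219 = 0.15 | 4.8% | about 6% |
| 14.3% v 0% | 0.37 | about 9% | 9.7% |
| 25% v 8.3% | 0.593 − 0.233 = 0.36 | about 11% | 11.8% |
| equal rates | about 0 | – | 5.0% |

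**3. Weaker link.** If exclusions fall at random within the poorer-responding half, the same three unequal scenarios give 0.09, 0.19 and 0.27 points, and 3.6%, 5.1% and 7.1% error in the favoured direction (nominal 2.5%).

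**4. Opposite direction.** With true means 6.5 and 4.5, and 14.3% of Arm B but none of Arm A excluded, the estimate is 2.0 − 0.37 = 1.63 points and power falls from about 92% to 84%.

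**5. All randomised patients, own scores.** In the three scenarios of step 2, keeping every patient's own score gives a difference of 0.01 to 0.02 points (a residual of stopping at 12 evaluable per arm) and error of 2.5–2.6% and 2.3% in the two directions.

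**6. Power when such patients are retained** (12 per arm analysed, SD 1.4 within each group, share q of each arm at an assumed lower mean reduction):

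| q | mean 2.5 | mean 1.0 |
|---|---|---|
| 5% | about 80% | about 73% |
| 10% | about 69% | about 58% |

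Most of the loss is added variance. At q = 5% and mean 2.5 the difference falls only to 0.95 × 2.0 = 1.90, but the Arm A variance rises from 1.96 to 1.96 + 0.05 × 0.95 × 4.0² = 2.72.

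**The case against.** **The simulated exclusions are not what Section 5 describes.** On the plan's inputs, excluding the lowest 14.3% of Arm B removes patients who improved by less than about 3.0 points; actual worsening would have a probability of about 0.07%. True worsening could be rarer or more extreme than modelled. This stands: the figures show how the mechanism works and do not estimate this trial's bias.

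**Under-use has no documented link to response.** This also stands. Section 1.4 hopes the vehicle will improve compliance, but no data show that adherence will differ by arm or track the outcome.

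**If nobody meets either rule, no harm is done.** True: the evaluable set would then be all randomised patients with data. The REU comparison and the daily diary scores also carry no separately stated exclusion. But REU is secondary, the diary comparison is not the week-4 change that Section 6.4 tests, and the plan must cover the case where the rules do apply.

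**An evaluable set is common in phase II.** It can stay as supportive. This design is nevertheless a randomised two-arm test at two-sided 5%.

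**Counting patients who add a drug as failures might seem the natural cure.** It is not a safe primary rule, because it converts an open-label prescribing decision into outcome. Setting the affected patients to zero change in the step 2 scenarios gives differences of −0.18, −0.33 and −0.52 points, with 3.4%, 4.4% and 7.2% error favouring the other arm. If the added drug is unrelated to response, the differences are about −0.30, −0.65 and −0.75 points, where exclusion would have been unbiased.

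**Conclusion.** The concern holds and should be fixed before analysis. It rests on the structure of the plan: exclusion and replacement after randomisation, one exclusion tied to worsening of the measured disease, open-label treatment, and no all-randomised primary analysis.

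Bias requires that exclusion differ by arm and be related to response; chance differences in counts under a common process do not produce it. The worst-case range of 0.15 to 0.37 points, against a 2.0-point target, depends on assumed rates.

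A reader might infer that the rule will favour Arm A, or that the trial is already biased. The documents support neither: they give no exclusion rates by arm, and step 4 shows the effect can run against Arm A as easily as for it.

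**What to change.** In Sections 6.4 and 6.6:

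1. Define the primary analysis as all randomised patients in their assigned arm, including any who are replaced, using the observed week-4 worst-sensitivity score regardless of adherence or added medication.
2. Collect that score from every patient who has not withdrawn consent, including those off protocol therapy.
3. State how missing week-4 scores are handled.
4. Keep the evaluable-only comparison as supportive. A failure rule such as zero change may be a sensitivity analysis only.

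In Section 6.2, restate power for this analysis.

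**Cost.** The changes are mostly wording, with some extra contact for patients off therapy. Under-users are identified at the week-4 visit, so their scores should normally be available. The real cost is power. At 12 per arm it can fall below the planned 80% (step 6), so the restatement may show that the sample size needs review. The observed score also includes any effect of the added drug, and the plan should say so.

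**Separate point to reconcile.** Section 5 keeps worsening patients who add a drug on treatment. Section 5.6 says "Subjects may be removed from the study in favor of clinical care should their symptoms worsen". Section 5.8 begins "Participants will be removed from study when any of the following criteria apply" and lists only loss to follow-up, consent withdrawal and death. These sections must be made consistent on whether worsening patients stay on treatment and on study, because that decides whether week-4 scores exist.

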6.2 Sample Size, Accrual Rate and Study Duration

The sample size was calculated based on the data by Rhodus et al., as to ensure at least 80% power and two-sided alpha of 0.05 in detecting a t difference of 2.0 points oral pain on an 11 point scale (VAS 0-10) between Arm A and B²⁴. The mean expected change for Arm A will be 6.5 points reduction with a standard deviation of 1.4 points. The mean expected change for Arm B will be 4.5 points reduction with a standard deviation of 1.4 points.

A total of 12 patients per arm will be enrolled (total of 24 subjects). The proposed sample size includes a loss of follow up of 5%. Approximately 75 patients per year are diagnosed with oral lichen planus at the Division of Oral Medicine and Dentistry (BWH)³². We anticipate the accrual rate will be approximately 5 patients per month, thus the accrual goal will be achieved in approximately five months.

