6.4 Analysis of Primary Endpoints

VAS scores will be summarized descriptively for each arm at pre-treatment, post-treatment, and pre-to-post treatment change. The pre-to-post treatment change will be compared between the arms using either Student's t-test or Mann-Whitney test, depending on the distribution of the data.

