8. RISKS AND DISCOMFORTS

8.1 Drug side effects and toxicities

Potential side effects with dexamethasone 0.5mg/5mL solution used as an oral topical rinse include an increased risk of developing oropharyngeal candidiasis and systemic absorption. All patients will be prescribed antifungal prophylaxis while on study with either fluconazole, clotrimazole or nystatin (see

CONFIDENTIAL

This document is confidential. Do not disclose or use except as authorized.

section 5.5). All participants will be informed that they may withdraw from the study at any time. As a topically applied agent, dexamethasone therapy can be discontinued at any time without any complications. Any noted clinical response will be expected to be reversed in such situations.

Prolonged application of potent topical corticosteroids (e.g., > 50 g of clobetasol propionate or > 500 g of hydrocortisone per week) may lead to short-term hypothalamic-pituitary-adrenal axis alteration. In our study, in case of any systemic absorption, the maximum dose would be 10.5 mg/week (5 mL x 0.1 mg/mL = 0.5 mg/rinse, 3 times/day = 1.5 mg, 7 days/week = 10.5 g). We do not expect there to be significant systemic absorption, and therefore do not expect systemic side effects of dexamethasone solution when used as a swish and spit. Mucolox™ is a vehicle for drug delivery used in compounding medications with ingredients expected to be harmless (see section 11.1.1).

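### Section 6.6 removes and replaces randomised patients who add an immunomodulatory medication or rinse too rarely, so the open-label primary comparison can omit treatment failures

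*Combined protocol and SAP*

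**What the plan says.** Section 6.6 names two groups that do not count for the primary endpoint and are replaced by new patients.

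- **Too little rinsing:** "Non-compliant patients who use the treatment fewer than 2 times a day for more than 2 weeks", judged from the diary at the week-4 visit. The prescribed use is three rinses a day for 28 days.
- **A new immunomodulatory medication**, systemic or topical in the mouth, started during the four weeks: "these patients will be regarded as unevaluable for the primary endpoint and will be replaced".

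Section 5 gives the setting for the second group: "If there is worsening of oral lichen planus that requires initiation of new immunomodulatory medications (systemic or topical), patients will remain on treatment". It repeats that they are unevaluable for the primary endpoint, but does not mention replacement.

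Section 5.6 lists reasons for stopping protocol therapy, among them "If the subject cannot tolerate the study rinses". It closes with: "Subjects may be removed from the study in favor of clinical care should their symptoms worsen", or if they have an adverse reaction. Section 5.8 limits the off-study reasons to loss to follow-up, withdrawal of consent for data submission, and death.

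Section 6.4 begins "VAS scores will be summarized descriptively for each arm" and then compares the change between arms by t-test or Mann-Whitney test. It names no analysis set. Sections 6.6 and 6.6.1 keep these patients in the toxicity evaluation.

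**The concern.** Both grounds arise after randomisation and both can be consequences of the assigned rinse. A patient whose disease worsens until another drug is needed has failed on treatment. Section 6.6 removes that patient and enrols another who may do better. The trial is open label, the score is patient-rated, and no criterion says when worsening requires new medication, so the decision that triggers exclusion can be made with the arm known.

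The arms differ only in the vehicle, and the primary objective covers tolerability as well as efficacy. If worsening or under-use is more frequent in one arm, the two evaluable groups are no longer the groups that were randomised. The reported effect would then describe only patients who kept rinsing and did not need added treatment. With 12 patients per arm, one or two such patients are enough to matter.

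**Working it through.** **Inputs (Section 6.2).** Expected reductions 6.5 (Arm A) and 4.5 (Arm B), SD 1.4, two-sided alpha 0.05, power at least 80%, 12 per arm, 5% loss to follow-up. The documents give no rate of added medication or under-use, so every count below is an assumption.

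**1. The plan's sample size.** The two-sample t-test needs 8.76, so 9 per arm, and 9/0.95 = 9.5, so 10. For a Mann-Whitney test at its worst-case efficiency of 0.864, 8.76/0.864 = 10.1, so 11, and 11/0.95 = 11.6, so 12. The stated 12 is reproduced by the second route; the protocol does not say which was used. With the planned inputs, t-test power is 91.7% at 12 per arm, 89.0% at 11 and 81.2% at 9. Replacement is therefore not needed to reach 80% when a few scores are missing.

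**2. Who meets the under-use rule.** In a 28-day diary, a patient who rinses as prescribed and then stops after day d has 28 − d days without rinsing. The rule needs 28 − d > 14, so d ≤ 13.

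**3. Effect on the difference.** Let kA and kB be the numbers of removed-type patients out of 12, with mean reductions mA and mB. If all randomised patients are kept:

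difference = 2.0 − kA(6.5 − mA)/12 + kB(4.5 − mB)/12

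Two outcomes are assumed for them: no change (mA = mB = 0), or half the planned reduction (3.25 and 2.25). For patients who stop rinsing, Section 8.1 makes a poor week-4 score plausible: "Any noted clinical response will be expected to be reversed in such situations".

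| Removed-type patients (A, B) | Evaluable only | All randomised, no change | All randomised, half kept |
|---|---|---|---|
| 1, 0 | 2.0 | 1.46 | 1.73 |
| 0, 1 | 2.0 | 2.38 | 2.19 |
| 1, 1 | 2.0 | 1.83 | 1.92 |
| 2, 0 | 2.0 | 0.92 | 1.46 |
| 0, 2 | 2.0 | 2.75 | 2.38 |
| 2, 2 | 2.0 | 1.67 | 1.83 |

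For example, (2, 0) with no change: 2.0 − 2 × 6.5/12 = 0.92.

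**4. Type I error in an unfavourable case.** Suppose both arms truly improve by 4.5 (SD 1.4) and exclusion removes exactly the worst responders, who are replaced to 12 (40,000 simulated trials, t-test).

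- Worst 1/12 of Arm A only: bias about 0.2 points, two-sided error 6.7%.
- Worst 2/12 of Arm A only: about 0.4 points, 11%.
- 2/12 in A and 1/12 in B: about 0.2 points, 6.6%.

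**5. Power when failures are kept.** Simulated chance of p < 0.05 favouring A, with removed-type patients drawn around the stated mean with SD 1.4:

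| Removed-type patients (A, B) | No change: t-test / Mann-Whitney | Half kept: t-test / Mann-Whitney |
|---|---|---|
| 1, 1 | 53% / 77% | 82% / 82% |
| 2, 2 | 20% / 55% | 71% / 71% |

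Fixing the change at exactly 0 moves the four no-change figures by no more than 2 percentage points. Most of the fall to 53% is added variance. With one zero-change patient per arm, the Arm A variance is 1.96 + 6.5²/12 = 5.48 and the Arm B variance is 1.96 + 4.5²/12 = 3.65, so the pooled SD is √4.56 = 2.14. At SD 1.4, a difference of 1.83 would still have 87% power.

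**The case against.** **Rescue may be rare.** There are only two visits, and Section 5 bars other agents meant to treat the lichen planus. Yet the same section and 6.6 then allow for such additions, so the plan expects some. The frequency stays unknown, which limits any claim about size but not the claim about the rule.

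**Added medication contaminates the week-4 score.** This stands. A failed patient who responds to a systemic drug would be credited to the rinse if the observed score were simply used. It argues for counting such patients as failures, not for dropping them. Section 6.6 also covers drugs started for unrelated illness, which are not failures.

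**The under-use rule targets non-compliers, and its threshold is lenient.** A reader might infer that patients who stop for intolerance are certainly excluded. The documents do not settle this: 6.6 states no exception, but it speaks of non-compliant patients, and 5.6 lists intolerance and unwillingness to comply separately.

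**Worsening patients leave the study.** A reader might infer from the end of 5.6 that they have no week-4 score. Section 5.8 does not list worsening or adverse reaction as off-study reasons, and the 5.6 sentence sits under a heading about stopping therapy. The two sections conflict; loss of the score is possible, not prescribed.

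**Other outcomes are intact.** Correct. Both rules concern the primary endpoint only. Nothing in them excludes these patients from the REU, COMDQLQ, daily-score or toxicity data.

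**Conclusion.** The point holds for the primary endpoint. The added-medication rule can remove treatment failures by the plan's own description. The under-use rule is a second post-randomisation exclusion of less certain meaning. No stated analysis brings either group back into the primary comparison.

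A reader might infer that the plan favours Arm A. The documents do not support that: the direction depends on which arm has more events, and no rates are given. Under the assumed outcomes, two removed-type patients in one arm put the all-randomised difference anywhere from 0.92 to 2.75, against 2.0 among evaluable patients. One in each arm leaves it at 1.83 to 1.92, so balanced events matter little for the mean. These figures illustrate sensitivity and are not estimates of bias. The change is worth making because it is a text edit to a small open-label trial and uses a visit already scheduled.

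**What to change.** In 6.6 and Section 5, delete the rules that make these patients unevaluable and replace them. State instead:

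> The primary analysis includes every randomised patient with a week-4 worst sensitivity score, in the assigned arm, whatever their rinse use; patients who started a new immunomodulatory medication for worsening lichen planus are counted as failures (change set to 0). Patients are not replaced on these grounds. Missing week-4 scores are reported by arm. Sensitivity analyses: observed week-4 scores regardless of added medication; change set to 0 for missing scores; evaluable patients only.

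In 5.6, change removal from the study to removal from protocol therapy, in agreement with 5.8, and state that these patients still attend the day 28 visit unless they withdraw consent.

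No visit is added, and enrolment stays at 24. The real cost is power, which falls when failures are kept: from about 92% (t-test, none) to about 53% by t-test or 77% by Mann-Whitney with one zero-change patient per arm, and to about 20% or 55% with two per arm. The sponsor should accept this openly or choose a larger sample. The failure label still rests on an unblinded decision to add medication, which is why the observed-score sensitivity analysis is needed.
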